8.3 Subject disposition

The number of subjects in the following categories will be summarized overall and by treatment group:

- Randomized
- Full Analysis Set (FAS)
- Per Protocol Analysis Set (PPAS)
- Safety Analysis Set
- PK Analysis Set
- ADA Evaluable Set

The number and percentage [REDACTED] of subjects in each of the following disposition categories will be summarized overall and by treatment group:

- Completed treatment at [REDACTED]
- Prematurely discontinued the treatment and the reasons for discontinuation
- Completed study (i.e., completed the wash-out period)
- Prematurely discontinued the study and the reason for discontinuation

A listing will be provided for subjects who discontinued treatment or who discontinued study with reasons for discontinuation.

8.4 Demographics and baseline characteristics

The demographics and baseline characteristics, medical history, prior and concomitant medications

Statistical Analysis Plan (SAP)

will be summarized by treatment group and overall for the FAS. Individual subject listings will be provided to support the summary tables.

8.4.1 Demographics

Age (years), height (cm), weight (kg) and other continuous demographic variables at Screening will be summarized descriptively. Gender, primary race, ethnicity and other categorical variables will be summarized using FAS.

Year of birth, age, gender, primary race, ethnicity, height and weight will be listed as part of demographic listing.

8.4.2 Baseline characteristics

Rheumatoid factor, body surface area (BSA) affected by psoriasis, tender joint counts, swollen joint counts, PGA of disease activity, PtGA of disease activity, patient's pain assessment, HAQ-DI, hsCRP, ESR, DAS28-CRP, LDI, LEI, PASI, SF-36, and PsAID at baseline will be summarized. [REDACTED] affected by psoriasis at baseline will be summarized as well.

8.4.3 Medical history

A summary of medical history will be presented by system organ class (SOC) and preferred term (PT) using the most recently available version of the Medical Dictionary for Regulatory Affairs® (MedDRA). A listing of medical history will be provided as well.

Quantiferon testing and chest X-ray results at screening will be summarized using frequency counts for FAS.

8.4.4 Prior and concomitant medications

Medications used in this study will be coded by using the World Health Organization Drug Dictionary and categorized as follows:

Prior medications and concomitant medications will be summarized descriptively using frequency tables by ATC class and preferred term by treatment group on the Safety Analysis Set. Prior medications are those with a stop date before the first dose of study drug, and concomitant medications are those with a stop date on or after the first dose of study drug or ongoing.

Details for imputing missing or partial start and/or stop dates of medication are described in [REDACTED]

Prior biologic and prior anti-TNF medications will be summarized in a separate table.

Statistical Analysis Plan (SAP)

8.5 Extent of exposure

8.5.1 Treatment Duration

Duration of study drug exposure [REDACTED] will be calculated as: [REDACTED]

[REDACTED] regardless of study drug interruption.

Study drug exposure will be summarised by treatment group on the Safety Analysis Set using descriptive statistics.

Exposure to randomized study drug will also be categorised in intervals [REDACTED]

8.5.2 Treatment Compliance

Study drug compliance will be calculated as: [REDACTED]

[REDACTED]. If only one syringe among the two is administered at a visit, the number of dose will be counted [REDACTED]. If both syringes are administered at a visit, the number of dose will be counted [REDACTED] total number of doses planned will count [REDACTED].

[REDACTED] If a subject discontinues treatment, the total number of doses will be counted from [REDACTED].

Study drug compliance will be summarized by treatment group by the number of subjects (n), mean, SD, median, min, and max. They will also be summarized in categories [REDACTED]

Study drug compliance summaries will be based on the Safety Analysis Set.

8.6 Efficacy analyses

8.6.1 Analysis methods

Analysis of proportions

The Cochran-Mantel-Haenszel (CMH) test, incorporating prior anti-TNF use [REDACTED] and Baseline weight [REDACTED], will be used to compare response rates of response-type variables between each of the respective active dose arms and placebo. In addition, the [REDACTED]

[REDACTED] Should assumptions per the [REDACTED] not be satisfied, pairwise comparisons will be based on [REDACTED] after collapsing across levels of the stratification factors. In this case, the response rate difference and CI will be based on normal approximation without considering stratification.

[REDACTED] repeated measures analysis of continuous endpoints

Statistical Analysis Plan (SAP)

A [REDACTED] analysis will be performed. The SAS procedure PROC MIXED will be used. The preferred model will include the fixed categorical effects of treatment, visit, treatment-by-visit interaction, prior TNF use [REDACTED] Baseline weight [REDACTED] as well as the continuous fixed covariates of baseline value. An unstructured matrix for the within-subject error variance-covariance will be used. The denominator degrees of freedom will be calculated according to the [REDACTED]

In case of non-convergence with the unstructured matrix, other within-subject error variance-covariance matrices, such as [REDACTED] will be considered.

The model will provide [REDACTED]

[REDACTED]
[REDACTED]

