4.2 Secondary efficacy endpoints [REDACTED]

The secondary efficacy endpoints of this study are:

Parts 1 and 2

- The proportion of subjects who achieve ACR20 [REDACTED]
- The proportion of subjects who achieve ACR50 [REDACTED]
ACR50 will be derived similarly as for ACR20 [REDACTED]
- The proportion of subjects who achieve ACR70 [REDACTED]
ACR70 will be derived similarly as for ACR20 [REDACTED]
- Change from Baseline in the individual components of ACR response at [REDACTED]
 - Tender joint counts [REDACTED]
 - Swollen joint counts [REDACTED]
 - PGA of disease activity (VAS)
 - PtGA of disease activity (VAS)
 - Patient's pain assessment (VAS)
 - Patient's self-assessed disability (HAQ-DI) [REDACTED]
 - Acute-phase hsCRP
 - ESR
- The proportion of subjects who require adjustment of background therapy [REDACTED]
- The proportion of subjects who achieve a DAS28-CRP [REDACTED]

The DAS28-CRP is a composite score derived from examination of the [REDACTED] for swelling and tenderness, CRP level, and patient global health assessment.

DAS28-CRP takes into account the following items:

- TJC28: [REDACTED]
- SJC28: [REDACTED]
- CRP: [REDACTED]
- GH: [REDACTED]

[REDACTED]
[REDACTED]

Statistical Analysis Plan (SAP)

If any of the components is missing, DAS28-CRP will be missing.

- The proportion of subjects who achieve MDA criteria at [REDACTED].

A psoriatic arthritis patient is defined as having a Minimal Disease Activity (MDA) response [REDACTED] when the patient meets [REDACTED] of the [REDACTED] following criteria: 1) tender joint count [REDACTED]; 2) swollen joint count [REDACTED] 3) PASI score [REDACTED] or BSA [REDACTED] 4) patient Arthritis Pain (VAS) [REDACTED]; 5) patient's global arthritis assessment [REDACTED] [REDACTED]; 6) HAQ-DI score [REDACTED]; 7) tender enthesal points [REDACTED] [REDACTED]

If there are sufficient non-missing components to determine whether the MDA is a response or non-response, then MDA is not missing. If the available non-missing components are not sufficient to determine the response status of MDA then it is considered missing.

- Change from Baseline in LDI and LEI at [REDACTED]

The Leeds dactylometer is a validated tool for assessing dactylitis. The dactylometer is used to measure the circumference of the base of the affected digit and is compared to the contralateral digit. [REDACTED]

[REDACTED] The final score for each digit is calculated and recorded on the CRF page, [REDACTED]

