7.2 Handling of missing data and outliers

7.2.1 Missing data analysis methods

In the primary analysis, ACR20 response rate at [REDACTED], missing values will be handled by setting the ACR20 value to nonresponsive. This approach will be used for all [REDACTED] endpoints (ACR20, ACR50, ACR70, DAS28-CRP, PASI75/90/100, and MDA) at all time points.

For a composite [REDACTED] endpoint (such as ACR20), if the values for any of the components at a time point are missing, the non-missing component variables will be used to determine the response status. If the response status cannot be determined due to missing components, then the composite response-type endpoint status is considered [REDACTED] for that time point.

For the HAQ-DI, LDI, LEI, SF-36 and PsAID instruments, rules suggested by the developers of these will be followed in calculating scores when individual question/items may be missing.

Details on handling missing data are outlined in [REDACTED].

In general, missing values for any of the endpoints will not be imputed when summarizing these endpoints using descriptive statistics.

In addition, missing values for safety endpoints will not be imputed.

Statistical Analysis Plan (SAP)

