8.6.3 Analysis of secondary endpoints

All secondary analyses will be performed using the FAS, unless otherwise stated. The response-type endpoints [REDACTED] will be analyzed based on the methods described for ACR20 in primary analysis. Continuous endpoints [REDACTED]

will be analyzed based on an MMRM analysis that includes the fixed effects of treatment, visit, treatment by visit interaction, prior anti-TNF use [REDACTED] Baseline weight [REDACTED] and Baseline value. Due to [REDACTED] Tildrakizumab and placebo group switching [REDACTED] Tildrakizumab [REDACTED], the comparisons between active drug and placebo will not be

Statistical Analysis Plan (SAP)

performed for the secondary endpoints collected after [REDACTED]. Response-type and continuous endpoints after [REDACTED] will be summarized descriptively. In addition, proportion of subjects who require adjustment of background therapy at [REDACTED] be presented with descriptive statistics.

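### MDA and, as it reads, DAS28-CRP response are end-state measures, but the readable plan tests them without any baseline disease activity; the cost is lost precision, not bias

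*SAP*

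**What the plan says.** Section 8.6.1 (Analysis of proportions) gives one method for every response-type variable: a CMH test "incorporating prior anti-TNF use" and baseline weight. The test "will be used to compare response rates of response-type variables between each of the respective active dose arms and placebo". Section 8.6.2 describes these two factors as the stratification factors.

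Section 8.6.3 says that the secondary response-type endpoints "will be analyzed based on the methods described for ACR20 in primary analysis". The list of endpoints in that sentence is redacted. Section 7.2.1, however, puts DAS28-CRP and MDA under the same non-responder rule as the other responses: "ACR20, ACR50, ACR70, DAS28-CRP, PASI75/90/100, and MDA) at all time points".

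Section 4.2 words the two endpoints as follows:

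- DAS28-CRP: "The proportion of subjects who achieve a DAS28-CRP", followed by a redaction.
- MDA: "A psoriatic arthritis patient is defined as having a Minimal Disease Activity (MDA) response" when a stated number of criteria is met. The criteria concern tender and swollen joints, PASI or BSA, pain, patient global, HAQ-DI and entheseal points. The cut-offs are redacted, and the readable text does not refer to change from baseline.

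For continuous endpoints, the repeated-measures model in 8.6.1 has treatment, visit, their interaction and the two factors, "as well as the continuous fixed covariates of baseline value". Section 8.4.2 lists baseline joint counts, pain, patient global, HAQ-DI, BSA, DAS28-CRP, LEI and other measures, ending "PASI, SF-36, and PsAID at baseline will be summarized".

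**The concern.** The CMH test suits ACR20/50/70 and PASI75/90/100, because each subject's own baseline is already in the definition. Section 4.1 works with percent change from baseline, and 4.3 defines the PASI responses as percent reductions. MDA is different: a subject who starts with few active joints and a low HAQ-DI is closer to the target than one who starts high. The same holds for DAS28-CRP response if it means reaching a fixed value.

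Baseline disease activity is therefore likely to predict both responses, and the readable analysis ignores it. What is at stake is the precision of two secondary endpoints in each of the four dose-placebo comparisons. The plan already accepts the principle for continuous endpoints and has the data, so nothing readable explains the omission here.

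**Working it through.** **Inputs from the SAP.** Testing is two-sided at alpha 0.05 (8.1). There are five treatments, hence four comparisons with placebo (3.3, 8.6.1.1). The CMH factors are prior anti-TNF use and baseline weight (8.6.1).

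**Inputs that have to be assumed.** The text of section 5 is not visible, so there is no planned power to reproduce. Assumptions: 50, 75 or 100 per arm; response 10% vs 25% or 20% vs 40%; correlation rho between baseline and the underlying visit score from 0.2 to 0.6.

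**Model.** Visit score L = rho·X + sqrt(1 − rho²)·e, where baseline X and error e are standard normal. A subject responds if L lies below Φ⁻¹(p), with p the arm's response rate. There are four equal strata and 5,000 trials per setting. The Monte Carlo SE of each power is at most sqrt(0.5 × 0.5/5,000) = 0.7 points.

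**Anchor.** The two-proportion formula at 75 per arm gives 76.7% (20% vs 40%) and 68.0% (10% vs 25%). The simulated CMH power agrees, at 75–77% and 67–68%.

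**Gain in power points, CMH to a logistic score test with strata and continuous baseline:**

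| n per arm | Rates | CMH power | rho 0.2 | 0.3 | 0.4 | 0.5 | 0.6 |
|---|---|---|---|---|---|---|---|
| 50 | 10% vs 25% | 50–52% | 3.1 | 3.1 | 5.1 | 6.5 | 10.0 |
| 50 | 20% vs 40% | 58–60% | 2.5 | 3.2 | 5.7 | 8.1 | 11.5 |
| 75 | 10% vs 25% | 67–68% | 2.2 | 3.1 | 5.0 | 6.7 | 10.0 |
| 75 | 20% vs 40% | 75–77% | 1.8 | 3.3 | 4.7 | 6.8 | 9.6 |
| 100 | 10% vs 25% | 80–81% | 1.5 | 2.2 | 3.7 | 5.5 | 8.5 |
| 100 | 20% vs 40% | 87% | 1.2 | 2.1 | 3.1 | 5.1 | 7.3 |

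**Standardised test.** A separate simulation at 75 per arm tested the marginal rate difference that the fix recommends. The gains over CMH were about 2.5 to 3 points at rho 0.3, 7 to 8 at 0.5 and 9 to 10 at 0.6.

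**How much is due to baseline.** Take 80 per arm, 30% placebo response, 10% scored as non-response and rho 0.5. Power is 77.7% for CMH, 78.7% for a logistic model with strata only, and 83.8% with baseline added. The change of test gives 78.7 − 77.7 = 1.0 point, and baseline gives 83.8 − 78.7 = 5.1 points.

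**Type I error.** At 75 per arm and 20% response in both arms (10,000 trials), CMH rejects in 5.1% and the adjusted score test in about 5.5%. For the standardised test the figures were 5.4–6.1%, against 5.0–5.5% for CMH.

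**Chance imbalance.** At 75 per arm, the difference in baseline means has SD sqrt(2/75) = 0.16 baseline SDs. An imbalance d shifts the rate by Φ(z_p) − Φ(z_p − rho·d). With p = 0.30 (z = −0.524) and rho = 0.5:

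- d = 0.16: 0.300 − Φ(−0.604) = 0.027, or 2.7 points.
- d = 0.32 (1.96 SD): 0.300 − Φ(−0.684) = 0.053, or 5.3 points.

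Over rates of 15% to 40% and rho 0.3 to 0.5, the shift is about 1 to 3 points at one SD and 2 to 6 at 1.96 SD. For scale, the SE of the unadjusted difference at 30% is sqrt(2 × 0.3 × 0.7/75) = 7.5 points, so 2.7 points is about 0.36 SE.

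**A simpler patch.** Adding a median split of baseline as a further CMH stratum changes power by only −1.0 to +4.7 points over the same settings.

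**The case against.** The strongest reply is that nothing is broken. Under randomisation the planned CMH test is valid, and leaving out a prognostic covariate costs some precision and nothing else. That stands. A reader might infer that the test is biased or rejects too often; the null results above do not support this.

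A reader might also count chance imbalance as a second harm. It is not: it belongs to the same sampling variance as the lost power, and the unadjusted CI already covers it.

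Nor does the SAP contradict itself by adjusting continuous endpoints and not these. A continuous covariate cannot enter a CMH test without being categorised.

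Redaction sets further limits. The DAS28-CRP cut-off, the endpoint list in 8.6.3 and a sentence on method in 8.6.1 are blacked out, so a further analysis cannot be excluded and the end-state reading of DAS28-CRP is an inference. Section 4.2 does say change from baseline where it means change, which supports that reading, but MDA is the clearer case.

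The simulation is also idealised. One latent score stands for both endpoints, whereas MDA counts criteria across joints, skin, pain, function and entheses. The gain for MDA from baseline DAS28-CRP plus HAQ-DI was not simulated.

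Finally, these are Phase 2b secondary endpoints, and the readable multiplicity procedure covers only ACR20. The consequence is therefore modest. What remains is an inexpensive precision gain that the plan does not take.

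**Conclusion.** The point holds as a minor improvement. The readable plan compares MDA and, as far as its wording shows, DAS28-CRP response with placebo without using a baseline value that is collected and likely to predict the result.

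Under the assumed 50 to 100 per arm, the power loss is about 1 to 4 points at rho 0.2 to 0.3, about 3 to 6 at 0.4, about 5 to 8 at 0.5 and about 7 to 12 at 0.6. Up to about 1 point of this comes from the change of test. No single figure can be stated as fact: a loss of 5 to 7 points, for example, needs rho near 0.4 to 0.5, and the SAP gives neither rho nor the sample size.

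The primary ACR20 test and the other ACR and PASI responses are not affected.

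**What to change.** In 8.6.3, for MDA and DAS28-CRP response at the visits compared with placebo, pre-specify before unblinding:

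- A logistic model with treatment, prior anti-TNF use, baseline weight and continuous baseline DAS28-CRP, plus baseline HAQ-DI for MDA.
- The standardised (marginal) response-rate difference over the FAS, with both the CI and the p-value taken from that same estimate using a robust SE. Pairing a conditional logistic p-value with a marginal CI would allow the two to disagree.
- Non-responder imputation unchanged, with the CMH result shown as supportive.

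ACR20/50/70 and PASI responses keep the CMH test. Section 8.6.4 needs no change, because its readable list of CMH-tested responses names only PASI.

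The cost is SAP wording and one extra model, with no new data. The downsides are that two secondary endpoints use a different model from ACR20, that a penalised fit may be needed if responders are few (the SAP should say when), and that small-sample type I error may lie slightly above 5%.

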8 STATISTICAL METHODS

8.1 General Statistical Conventions

All statistical procedures will be completed using SAS version 9.4 or higher.

Unless otherwise stated, all statistical testing will be two-sided and will be performed using a significance (alpha) level of 0.05.

Continuous variables will be summarized using descriptive statistics, including number of subjects (n), mean, median, standard deviation (SD), minimum and maximum. One additional decimal point for mean and median and [REDACTED] for SD will be used.

For categorical variables, summaries will include counts of subjects and percentages. [REDACTED]

For summary purposes, baseline will be defined as the last available value prior to the date of first IMP administration; all summaries will be presented by treatment group, unless otherwise specified.

For reporting purpose, summary tables for efficacy variables and safety variables will be displayed by nominal visit as appropriate. Unscheduled assessments will not be included in the summary tables, but will be in data listings.

All subject data, including those derived, will be presented in individual subject data listings. Unless otherwise stated, unscheduled visit results will be included in date/time chronological order, within patient listings only. All listings will be sorted by treatment group, subject number, date/time and visit. The treatment group as well as patient's sex and age will be stated on each listing. Unless otherwise stated, data listings will be based on all randomized subjects.

The treatment groups will be displayed in the format below in tables including [REDACTED]:

- [REDACTED]
- [REDACTED]
- [REDACTED]
- [REDACTED]
- [REDACTED]

The treatment groups will be displayed in the format below for tables including [REDACTED] and all listings:

Statistical Analysis Plan (SAP)

- [REDACTED]
- [REDACTED]
- [REDACTED]
- [REDACTED]
- [REDACTED]

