8.6.4 Analysis of exploratory endpoints

The response-type endpoints (PASI 75/90/100) up to [REDACTED] will be analyzed based on the CMH methods described for ACR20. Continuous endpoints ([REDACTED] up [REDACTED] will be analyzed based on an MMRM analysis as described for secondary endpoints. Response-type and continuous endpoints after [REDACTED] will be summarized descriptively.

In addition, there will be sub-groups of patients in Part 3 who either did or did not receive any new therapy for PsA and these will be analyzed separately for ACR20, ACR50, and ACR70.

All the exploratory analyses will be based on the FAS except PASI, which will be based on the subjects in █ who have baseline █

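### The fallback confidence interval for response rates is an unnamed normal approximation, which may be too narrow at very low, unequal rates and, if plain Wald, has zero width when neither arm has a responder

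*SAP*

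**What the plan says.** SAP section 8.6.1 (Analysis of proportions) names a CMH test with prior anti-TNF use and baseline weight. It "will be used to compare response rates of response-type variables between each of the respective active dose arms and placebo". The section then sets a fallback. Should the assumptions of a redacted criterion "not be satisfied, pairwise comparisons will be based on" a redacted test, carried out "after collapsing across levels of the stratification factors". The sentence on estimation is not redacted: "In this case, the response rate difference and CI will be based on normal approximation without considering stratification".

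The rule is not confined to ACR20.
- Section 8.6.3 says of the secondary response-type endpoints that they "will be analyzed based on the methods described for ACR20 in primary analysis".
- Section 8.6.4 says: "The response-type endpoints (PASI 75/90/100) up to [REDACTED] will be analyzed based on the CMH methods described for ACR20".
- Section 7.2.1 counts missing responses as non-response for "endpoints (ACR20, ACR50, ACR70, DAS28-CRP, PASI75/90/100, and MDA) at all time points", which can only lower the analysed rates.

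The readable text does not say whether the normal approximation is plain Wald or continuity-corrected, or what is reported when an arm has no responders.

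**The concern.** Collapsing strata after a failed assumption suggests that the fallback is meant for small counts. A normal-approximation interval for a difference in proportions is least reliable with small counts, because it estimates the variance from the observed proportions alone. An arm with no responders contributes zero variance, and two such arms give an interval of zero width.

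What is at stake is the reported interval for rarely met endpoints, possibly ACR70 or PASI90/100 (the SAP gives no rates). A reader could take a too-narrow or zero-width interval as strong evidence of no difference. Dropping the stratification in this branch matches the collapsed comparison and is not criticised. Only the type of interval is.

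**Working it through.** **Inputs.** The SAP gives no readable arm size, response rate or coverage figure, so there is nothing of its own to reproduce.
- Confidence level: 95%, inferred from section 8.1 ("all statistical testing will be two-sided and will be performed using a significance (alpha) level of 0.05"), since the level of this interval is redacted.
- Arm sizes: n = 20, 40, 60 and 80 per arm, equal allocation (assumed).
- True rates: nine assumed pairs, from very low to ordinary.

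**Formulas.** With x1 and x2 responders, p = x/n, d = p1 − p2 and z = 1.96:
- Plain Wald: d ± z·√[p1(1−p1)/n + p2(1−p2)/n].
- Continuity-corrected Wald: the half-width is increased by (1/n + 1/n)/2 = 1/n.
- Newcombe: combines the two single-arm Wilson limits.
- Miettinen-Nurminen: inverts the score test with its N/(N−1) variance factor, where N = 2n.

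Coverage is the exact sum of binomial probabilities over all tables whose interval contains the true difference.

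**Step 1: no responder in either arm, 0/40 v 0/40.**
- Plain Wald: both variance terms are 0, so the interval is [0, 0]. This holds for any n.
- Continuity-corrected: ±1/40 = ±2.5 points.
- Newcombe: the Wilson upper limit is z²/(n + z²) = 3.84/43.84 = 0.088, so ±8.8 points.
- Miettinen-Nurminen: the limit solves n·D·(79/80)/(1−D) = z², so D = 3.84/(3.84 + 39.5) = 0.089, or ±8.9 points.

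**Step 2: how often that table occurs.** At 5% v 1% with n = 20, the probability is 0.95^20 × 0.99^20 = 29.3%. For n = 40, 60 and 80 it is 8.6, 2.5 and 0.7%. At 10% v 2% it is 8.1, 0.7, 0.05 and below 0.01%.

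**Step 3: coverage at low, unequal rates (%, nominal 95).**

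| Rates | Interval | n=20 | n=40 | n=60 | n=80 |
|---|---|---|---|---|---|
| 5% v 1% | plain Wald | 69.9 | 86.9 | 93.1 | 90.4 |
| | plain Wald, 0 v 0 left out | 98.8 | 95.1 | 95.5 | 91.0 |
| | continuity-corrected | 99.97 | 91.3 | 95.2 | 97.7 |
| 10% v 2% | plain Wald | 87.1 | 91.0 | 92.3 | 93.5 |
| | plain Wald, 0 v 0 left out | 94.8 | 91.6 | 92.4 | 93.5 |
| | continuity-corrected | 91.6 | 98.0 | 97.6 | 97.2 |
| 10% v 5% | plain Wald | 85.8 | 93.9 | 94.3 | 94.5 |
| | plain Wald, 0 v 0 left out | 89.7 | 94.1 | 94.3 | 94.5 |
| | continuity-corrected | 99.7 | 97.5 | 97.8 | 97.5 |

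The rows without 0 v 0 divide by the remaining probability: at 5% v 1%, n = 20, 0.699/(1 − 0.293) is about 0.988. So the worst figure is almost wholly the zero-width interval. The shortfalls at 5% v 1% with n = 80, and at 10% v 2% from n = 40, are not. Over these twelve cells Newcombe covers 96.1–99.9% and Miettinen-Nurminen 93.6–99.8%.

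**Step 4: where plain Wald holds up.**
- Equal low rates, n = 20/40/60/80: 2% v 2% gives 99.9/99.3/98.0/96.9%; 5% v 5% gives 98.8/95.7/94.0/95.0%; 10% v 10% gives 96.0/94.1/94.0/94.8%. Here [0, 0] happens to contain the true difference of zero.
- Ordinary rates (20% v 10%, 30% v 15%, 50% v 30%): 93.6–94.8%.

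**The case against.** The strongest objection is that both premises are unseen. The trigger is redacted, and so is nearby text that may describe the main interval method. The phrase normal approximation also fits a continuity-corrected interval. With that correction, ten of the twelve low, unequal cells reach 95% and the 0 v 0 interval is no longer degenerate. A criterion on stratified counts can also fail because strata are thin while the collapsed table is adequate; collapsing is itself a remedy for that. The coverages above are unconditional, so they do not describe results inside the fallback branch. The worst figures need small arms and rates that the document does not give. Section 8.6.4 carries over the CMH methods, and whether that includes the non-CMH fallback is not explicit. Finally, no decision is shown to hang on these intervals, because the visible multiplicity procedure in section 8.6.1.1 works on p-values for ACR20.

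Most of this stands as a limit on weight and is why the point is minor. It does not remove the point. The estimation sentence is readable and settles on a normal approximation without saying which. The weakness does not need a sparse-count trigger, because plain Wald behaves this way on any collapsed table with very few responders. The continuity-corrected reading also falls short in two cells (91.3% at 5% v 1%, n = 40; 91.6% at 10% v 2%, n = 20).

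**Conclusion.** The concern holds in its conditional form, as a minor point held with medium confidence. If the fallback interval is plain Wald, it under-covers at very low, unequal rates: 85.8–93.5% in the low, unequal cells with fewest expected responders, apart from 69.9% at 5% v 1% with n = 20, and close to nominal by 10% v 5% from n = 40. It is [0, 0] whenever neither arm has a responder. If the trigger is a sparse-count rule, these are the kinds of table the branch would meet.

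The effect is limited to the reported intervals of low-rate secondary and exploratory endpoints. The primary ACR20 result and the fallback p-value are not shown to be affected. Arm sizes, response rates, the 95% level, the trigger and the Wald form are all assumptions. The redactions are not part of the criticism.

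**What to change.** In the fallback sentence of SAP section 8.6.1, replace the normal approximation with a named unstratified score-type interval, Newcombe or Miettinen-Nurminen, computed on the same collapsed table as the fallback comparison. This also settles what is reported when neither arm has a responder.

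The cost is one sentence, and wider intervals at low rates, slightly conservative with Newcombe. At 10% v 2% the mean width goes from 19.8 points (plain Wald) to 24.6 (Newcombe) at n = 40, and from 14.3 to 16.1 at n = 80. At ordinary rates there is almost no change: at 30% v 15%, 35.5 v 35.4 points at n = 40 and 25.3 v 25.2 at n = 80. If the redacted trigger proves to be something other than a sparse-count rule, the change does no harm.
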